9.3.3.2 Relationship to Study Medication

The assessment of relationship of AEs to the administration of study drug is a clinical decision based on all available information at the time of the completion of the CRF. Investigators must systematically assess the causal relationship of AEs to the study drug using the following definitions. Decisive factors for the assessment of causal relationship of an AE to SNS-301 include, but may not be limited to, temporal relationship between the AE and SNS-301, known side effects of SNS-301, medical history, concomitant medication, course of the underlying disease, and study procedures.

Not Related:

Not reasonably suspected to be related to the study drug. The AE could not medically (pharmacologically/clinically) be attributed to the study drug under investigation in this clinical study protocol. A reasonable alternative explanation must be made available.

Related:

Suspected related to the study drug. The AE could medically (pharmacologically/clinically) be attributed to the study drug under investigation in this clinical study protocol.

9.3.4 Adverse Event Reporting

9.3.5 Serious Adverse Event Reporting

All SAEs occurring during the course of the clinical trial from signing the informed consent through the end of the study will be collected and reported (e-mail) by the Investigator to the Pharmacovigilance Team assigned (see contact information below) by completing a Serious Adverse Event Report Form within 24 hours or next business day, whichever is shorter, from the point in time when the Investigative site becomes aware of the SAE. All SAEs must be reported whether or not considered causally related to the study treatment. The information collected will include patient number, a narrative description of the event and an assessment by the Investigator as to the severity of the event, and relatedness to study drug. Include copies of relevant source documents. (e.g., progress notes, autopsy reports, laboratory and diagnostic test results, discharge summaries) Follow-up information on the SAE may be requested by the Sponsor.

SAEs should be reported to:

Global Safety and Pharmacovigilance, Advanced Clinical

Email: [contact]

The minimum required information for an initial report of an SAE is:

- Reporter name and contact number,
- Protocol number,
- Site and patient ID information, and
- The SAE term with a brief summary of the event including the causality assessment, if possible.

Contact the Sponsor-designated Medical Monitor or designee using the contact information and instructions provided supplemental to this protocol.

The Sponsor must notify FDA and all participating Investigators (i.e., all Investigators to whom the Sponsor is providing drug under its INDs or under any Investigator's IND) in an IND safety report of potential serious risks, from clinical trials or any other source, as soon as possible, but in no case later than 15 calendar days after the Sponsor determines that the information qualifies for reporting under paragraph (c)(1)(i), (c)(1)(ii), (c)(1)(iii), or (c)(1)(iv) of 21CFR 312.32. The Sponsor must identify all IND safety reports previously submitted to FDA concerning a similar suspected adverse reaction and must analyze the significance of the suspected adverse reaction in light of previous, similar reports or any other relevant information.

In addition, The Sponsor must also notify FDA of any unexpected fatal or life-threatening suspected adverse reaction as soon as possible but in no case later than 7 calendar days after the Sponsor's initial receipt of the information.

9.3.6 Serious and unexpected suspected adverse reaction

The Sponsor must report any suspected adverse reaction that is both serious and unexpected. The Sponsor must report an adverse event as a suspected adverse reaction only if there is evidence to suggest a causal relationship between the drug and the adverse event, such as:

1. A single occurrence of an event that is uncommon and known to be strongly associated with drug exposure (e.g., angioedema, hepatic injury, Stevens-Johnson Syndrome);
2. One or more occurrences of an event that is not commonly associated with drug exposure, but is otherwise uncommon in the population exposed to the drug (e.g., tendon rupture);

An aggregate analysis of specific events observed in a clinical trial (such as known consequences of the underlying disease or condition under investigation or other events that commonly occur in the study population independent of drug therapy) that indicates those events occur more frequently in the drug treatment group than in a concurrent or historical control group.

Reports will be made as soon as possible, and in no event later than seven (7) calendar days if the event is a death or is life threatening and 15 calendar days for all other reportable events after the Sponsor's initial receipt of the information. Each written notification may be submitted on a CIOMS-I form, a FDA Form 3500A, or in a tabular or narrative format in accordance with regulatory requirements. In each report, the Sponsor will identify all safety reports previously filed concerning a similar suspected adverse reaction and will analyze the significance of the suspected adverse reaction in light of the previous, similar reports.

Follow-up information to a safety report will be submitted as soon as the relevant information is available. If the results of a Sponsor's investigation show that an AE not initially determined to be reportable is, in fact, reportable, the Sponsor will report the suspected AE in a written safety report as soon as possible, but in no event later than 15 calendar days after the determination is made. Results of investigations of other safety information will be submitted, as appropriate, in an information amendment or annual report.

If an investigator receives an IND safety report or other specific safety information (e.g., SUSAR, summary or listing of SAEs) from the sponsor, the investigator will review and file along with the Investigator's Brochure and will notify the IRB/IEC, if appropriate according to local regulations. In these instances, the ICF may need to be revised to inform the patient of any new safety concern.

9.3.7 *Unanticipated (Serious) Adverse Device Effect (UADE)*

A UADE is any serious adverse effect on health or safety or any life-threatening problem or death caused by, or associated with, a device, if that effect, problem, or death was not previously identified in nature, severity, or degree of incidence in the investigational plan or application (including a supplementary plan or application), or any other unanticipated serious problem associated with a device that relates to the rights, safety, or welfare of patients.

Per the definition above, a UADE is a type of SAE that requires expedited reporting on the part of the Sponsor. As a reminder, all SAEs regardless of relationship to device, drug or procedure are to be reported to Sponsor by the trial Investigator within 24 hours. Sponsor will assess each device related SAE to determine if anticipated based on prior identification within the investigational plan. The Sponsor may notify a regulatory authority within the time frame specified by local requirements but no later than 10 business days for UADE.

UADE form should be reported to:

Global Safety and Pharmacovigilance, Advanced Clinical

Email: [contact]

9.3.8 *Dose-Limiting Toxicities*

DLTs are events [toxicities] specifically identified in this protocol that must be reported in an expeditious manner. Information regarding DLTs should be recorded on a DLT Confirmation Worksheet and faxed or emailed within 24 hours of site personnel becoming aware of the event. DLTs may or may not be serious adverse events as an Unexpected Adverse Event. DLTs are assessed up to week 6 for patients enrolled in the Safety Run-In period.

Any of the following, if judged to be associated with SNS-301 (i.e., possibly related, probably related, or related to), will be considered a DLT which are based on the NCI-CTCAE V5.0 criteria:

- 1) Grade 4 non-hematological toxicities (excluding alopecia) of any duration
- 2) Grade 3 non-hematologic (non-laboratory) toxicity lasting > 3 days despite optimal supportive care
- 3) Any Grade 3 or Grade 4 non-hematologic laboratory value if: a). Medical intervention is required to treat the patient; b), the abnormality leads to hospitalization; c). The abnormality persists for >1 week.
- 4) Grade 4 hematologic toxicity, other than those specified in criteria 5 and 6 below, lasting > 7 days
- 5) Grade 3 or Grade 4 febrile neutropenia of any duration
- 6) Grade 3 thrombocytopenia in combination with a grade 3 or greater blood and lymphatic system disorder

- 7) Grade 3 AST or ALT that is associated with a grade 2 rise in bilirubin

Additional information regarding reporting DLTs may be required by the Sponsor.

Completed DLT Confirmation Worksheets should be faxed or e-mailed to:

Global Safety and Pharmacovigilance, Advanced Clinical

Email: [contact]

9.3.9 *Stopping Rules*

Stopping rules for adverse events will be employed for this trial. The trial will be stopped if any adverse experience of any related death, grade 4 autoimmune toxicity or any grade 4 toxicity that is considered to have a causal relationship to study drug. Any related death, grade 4 autoimmune toxicity and any grade 4 toxicity that is considered to have a causal relationship to study drug will be submitted to regulatory agencies within the expedited safety reporting criteria.

9.3.10 *Adverse Events of Special Interest*

Adverse events that occur during or within 24 hours after study treatment administration and are judged to be related to study treatment infusion should be captured as a diagnosis (e.g., “infusion-related reaction”) on the Adverse Event eCRF. If possible, avoid ambiguous terms such as “systemic reaction.” If a patient experiences both a local and systemic reaction to the same dose of study treatment, each reaction should be recorded separately on the Adverse Event eCRF.

Systemic administration site reactions will be considered an AESI. The area around the administration site will be assessed by a medically qualified individual for adverse reactions at least 30 minutes post study drug administration. The Investigator will grade any ASRs according to the NCI-CTCAE V5.0 (excluding the actual expected micro-injection punctures).

Patients will be required to report any change in the administration site and return to the clinic for evaluation by the Investigator.

Adverse events of special interest (AESI) are required to be reported by the investigator to the Sponsor immediately (i.e., no more than 24 hours after learning of the event; see Section [Adverse Event Reporting](#) for reporting instructions).

AESI s should be reported to:

Global Safety and Pharmacovigilance, Advanced Clinical

Email: [contact]

9.3.11 *Guidance for Investigators for Patients on Anti-coagulants*

Based on the preclinical data and the role of ASPH in post-translational modification of proteins involved in the clotting and anticoagulant pathways (Factors VII, IX, X , Protein C), there may a potential for abnormal coagulation with SNS-301. Should there be a clinically significant AE or SAE recorded, such as clinically noted bleeding, administration of SNS-301 will be held until the AE/SAE returns to baseline. Should there be two individual events of SNS-301 interruption for the

same patient, then SNS-301 will be discontinued after consultation with the Medical Monitor and Sponsor. Clinical management and further workup of the coagulation pathway disturbance will be at the discretion of the treating physician.

9.3.12 *Reporting of Pregnancy*

If pregnancy occurs in a female patient, or female partner of a male patient while the patient is on treatment or until six months after the last dose, the sponsor will be notified within 24 hours of learning of the pregnancy. The pregnancy will be followed until birth or termination. Abnormal pregnancy outcomes (e.g., spontaneous abortion, fetal death, stillborn, congenital anomalies, ectopic pregnancy) are considered SAEs.

Pregnancy should be reported to:

Global Safety and Pharmacovigilance, Advanced Clinical

Email: [contact]

9.3.13 *Time Period and Frequency for Event Assessment and Follow-Up*

All AESIs and SAEs, including death due to any cause, that occur during this study and until 90 days after the last dose of study treatment or until the start of a new anti-cancer treatment, whichever comes first, whether or not expected and regardless of causality, must be reported to the Medical Monitor immediately upon discovery of the event, using an SAE Form.

All AEs will be collected from the time of signing the informed consent form until 30 days after the last dose after the last dose of study treatment or until the start of a new anti-cancer treatment, whichever comes first.

Any medical condition that begins after obtaining informed consent will be recorded the AE section of the CRF. If the patient's condition worsens during the study, the event will be recorded as an AE.

All AEs/SAEs will be captured on the appropriate case report form. Information to be collected includes event description, date of onset, severity, relationship to study intervention and date of resolution.

10. Statistical Considerations

10.1 Statistical Hypotheses

Cohort A

Thirty (30) patients will be enrolled in a two-stage design, with 15 patients in the first stage and 15 patients in the second stage to assess the null hypothesis that the objective response rate per iRECIST is 5%, versus the alternative hypothesis that the ORR is 18%, as described in Section 10.2.

Cohort B

Thirty (30) patients will be enrolled in a two-stage design, with 15 patients in the first stage and 15 patients in the second stage to assess the null hypothesis that the objective response rate per

iRECIST is 13.3%, versus the alternative hypothesis that the ORR is 29%, as described in Section 10.2.

10.2 Sample Size Determination

Adverse events will be continuously monitored. Among the first phase of 15 patients, for adverse events that occur at an incidence of 18% the probability of observing at least one event is approximately 95%. Among all 60 patients, for adverse events that occur at an incidence of 5% the probability of observing at least one event is approximately 95%.

The sample size for each cohort and stage is based on Simon's two-stage design for tests of one proportion.

Cohort A

To evaluate the primary endpoint of objective response rate per iRECIST at 12 weeks with a null hypothesis of an objective response rate (ORR) of 5% and an alternative hypothesis of an ORR of 18%, 30 patients in a two-stage design with 15 patients in the first stage and 15 patients in the second stage will be enrolled. At the first stage analysis if at least 1 response is observed out of 15 patients, the study will continue through the second stage. At the second stage analysis, if at least 4 responses are observed out of 30 total patients, the null hypothesis will be rejected and further research considered warranted. The overall power for objective response rate at 12 weeks is 80%. The overall type I error, the chance of incorrectly rejecting the null hypothesis is 6% (targeted alpha of 0.10). The probability of stopping at the first stage under the null hypothesis is 46%. The operating characteristics of this design are calculated using the exact binomial distribution.

Cohort B

To evaluate the primary endpoint of objective response rate per iRECIST at 12 weeks with a null hypothesis of an objective response rate (ORR) of 13.3% and an alternative hypothesis of an ORR of 29%, 30 patients in a two-stage design will be enrolled, with 15 patients in the first stage and 15 patients in the second stage. At the first stage analysis if at least 2 responses are observed out of 15 patients, the study may continue through the second stage. At the second stage analysis, if at least 7 responses are observed out of 30 total patients, the null hypothesis will be rejected and further research considered warranted. The overall power for objective response rate at 12 weeks is 80.1%. The overall type I error, the chance of incorrectly rejecting the null hypothesis is 9.2% (targeted alpha of 0.10). The probability of stopping at the first stage under the null hypothesis is 38.8%. The operating characteristics of this design are calculated using the exact binomial distribution.

10.3 Populations for Analyses

The following analysis populations will be used for presentation of the data:

Safety Analysis Set: The safety analysis will be based on the Safety Analysis Set, which comprises all patients who receive at least 1 dose of the study treatment or component of the study treatment.

Efficacy-Evaluable Analysis Set: All patients who receive at least 1 dose of the study treatment or component of the study treatment and have a post baseline response assessment per iRECIST at Week 12. Patients who discontinued prior to Week 12 due to disease clinical progression will be included. Patients who do not have a post baseline response assessment conducted will not be included.

Safety Run-In Set: All patients who receive at least 1 dose of the study treatment or component of the study treatment apart of the safety run-in.

Immunologic Analysis Set: All patients who receive at least 1 dose of the study treatment or component of the study treatment and have at least one valid post-baseline immunologic assessment available.

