10.4 Statistical Analyses

The statistical analysis plan will be developed and finalized before database lock and will describe the patient populations to be included in the analyses, and procedures for accounting for missing, unused and spurious data.

The statistical analysis plan will specify how lost to follow-up patients will be addressed in the primary analysis.

10.4.1 *General Methods*

All summarizations will be presented separately for each cohort, and over all subjects combined.

For continuous variables, descriptive statistics (number (n), mean, median, standard deviation, minimum and maximum) will be presented. For categorical variables, frequencies and percentages will be presented. For time-to-event variables, percentages of patients experiencing that event will be presented and median time-to-event will be estimated using the Kaplan-Meier method. As appropriate, a 95% CI will be presented. Graphical displays will be presented, as appropriate.

Patients demographic characteristics including age, gender, and race will be analyzed, with categorical variables summarized in frequency tables while continuous variables summarized using mean (standard deviation) and median (range).

All data collected will be presented in by-patient data listings.

10.4.2 *Efficacy Analyses*

ORR is defined as the proportion of patients with a confirmed best response of iCR or iPR by iRECIST. Objective response rate will be estimated, and 90% CI based on the exact binomial distribution will be presented by cohort and overall, including number and percent of patients in each overall response category.

The primary analysis will be based on objective response at Week 12. An additional analysis of ORR based on best objective response during the study will be performed.

DOR, DCR, PFS, and OS will also be calculated, defined as follows:

- DOR: time from date of first response to date of progression, where patients without progression are censored at date of last valid disease assessment
- DCR: proportion of patients with SD or better (PR and CR). SD for at least six months
- PFS: time from date of start of treatment to date of progression, where patients without progression are censored at date of last valid disease assessment
- OS: time from date of start of treatment to date of death or censored at date of last contact

Efficacy analyses will be performed using the efficacy-evaluable analysis set.

10.4.3 *Safety Analyses*

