### *Efficacy-Evaluable Analysis Set*

The Efficacy-Evaluable Analysis Set comprises all patients who receive at least 1 dose of the study treatment or component of the study treatment and have a post baseline response assessment per iRECIST at Week 12. Subjects who discontinued prior to Week 12 due to radiological disease progression will be included. Subjects who do not have a post baseline response assessment conducted will not be included in the analysis of efficacy.

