## 9. STATISTICAL/ANALYTICAL ISSUES

### 9.1 Handling of Dropouts or Missing Data

All available data will be presented on the data listings as collected.

Algorithms for imputing partial or missing dates related to AEs and prior/concomitant medications are shown below.

Table 3      Imputation Rules for Partially Missing Dates

Variable	Missing Day	Missing Day, Month	Missing Day, Month, Year
Date of Last Therapy/Date of Initial Diagnosis	Assign 1	Assign January 1 if prior to date of informed consent, otherwise use date of informed consent	Missing (do not impute)
Adverse Event/Medication Start Date	Assign first day of month unless it is the month of first dose of study medication. Otherwise, assign date of first dose of study medication.	Assign January 1 unless the year is year of first dose of study medication Otherwise, assign date of first dose of study medication.	Assign date first dose of study medication.
Adverse Event/Medication End Date	Assign the last day of the month or end of study date, whichever is earlier.	Assign December 31 or end of study date, whichever is earlier.	If ongoing, end date is missing. Otherwise, assign end of study date.

Every effort to re-contact the patient lost to follow-up patients will be made, to identify the reason why he/she failed to attend the visit, and to determine his/her health status, including at least his/her vital status. Data from lost to follow-up subjects to the date of last recorded contact will be included in the analyses.

Non-evaluable patients will be replaced.

Sponsor: Sensi Biotherapeutics

Protocol: SNS301-2-2

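### Dosed patients with neither progression nor a Week 12 scan are dropped from the primary ORR instead of counted as non-responders, so the ORR is inflated relative to all treated patients

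*Protocol*

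**What the plan says.** Protocol 10.3 and SAP 4 build the Efficacy-Evaluable Analysis Set from dosed patients who have an iRECIST assessment at Week 12. The only patients kept without one are those who left early because of progression (the documents describe that progression differently, which is a separate matter). Protocol 10.3 then says "Patients who do not have a post baseline response assessment conducted will not be included"; SAP 4 says "Subjects who do not have a post baseline response assessment conducted will not be included in the analysis of efficacy". SAP 7.1 bases the primary ORR on this set.

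Protocol 10.4 promises: "The statistical analysis plan will specify how lost to follow-up patients will be addressed in the primary analysis". SAP 9.1 offers only this: "Data from lost to follow-up subjects to the date of last recorded contact will be included in the analyses". It does not say whether a lost patient counts as a non-responder or leaves the ORR. SAP 7.1 treats dropouts as non-responders for DCR but has no matching line for ORR.

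On replacement, SAP 9.1 says "Non-evaluable patients will be replaced", and Protocol 5.2 and SAP 2.2 say the same. Protocol 8.2 says that a patient who has received study treatment and then discontinues is not replaced, apart from run-in patients who withdraw for reasons other than toxicity.

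**The concern.** A dosed patient who has not progressed, but who dies, withdraws, is lost, or stops for toxicity and misses the Week 12 scan, has no Week 12 response. Leaving that patient out of the denominator, rather than scoring a non-response, pushes the ORR up.

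The decisions turn on very few responses: 1 of 15 and then 4 of 30 in Cohort A, 2 of 15 and then 7 of 30 in Cohort B. If each excluded patient is also replaced, a non-responder is exchanged for a new chance of response, and a false go becomes more likely when the null rate describes all treated patients.

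**Working it through.** **Inputs.** Cohort A (Protocol 10.1 and 10.2): the null ORR per "iRECIST is 5%, versus the alternative hypothesis that the ORR is 18%, as described in Section 10.2". Stage 1: "At the first stage analysis if at least 1 response is observed out of 15 patients, the study will continue through the second stage". Final: "if at least 4 responses are observed out of 30 total patients, the null hypothesis will be rejected". Cohort B (Protocol 10.1 and 10.2): null 13.3%, alternative 29%, continue with at least 2 of 15, reject with at least 7 of 30. The excluded share d is in neither document; 5% to 20% is an assumed range.

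**Step 1: reproduce the plan.** With c1 the stage 1 minimum, c the final minimum and p the response rate, P(reject) = sum over x from c1 to 15 of P(X1 = x) × P(X2 ≥ c − x), where X1 and X2 are independent Binomial(15, p).

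- Cohort A (c1 = 1, c = 4): type I error 5.82%, power 80.0%, early stopping under the null 0.95^15 = 46.3%. Stated: 6%, 80%, 46%.
- Cohort B (c1 = 2, c = 7): type I error 9.17%, power 80.1%, early stopping 38.8%. Stated: 9.2%, 80.1%, 38.8%.

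All stated figures reproduce for 15 and 30 patients who respond at the null rate.

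**Step 2: effect on the estimate.** Take every excluded patient as a non-responder. If the rate among all treated patients is p, the rate among evaluable patients is p/(1 − d). At d = 10% the factor is 1/0.9 = 1.11, so 5% becomes 5.6% and 13.3% becomes 14.8%. In counts, 30 evaluable patients then need 30/0.9 = 33.3, so about 34 treated. Four responses read as 4/30 = 13.3% rather than 4/34 = 11.8%; seven read as 7/30 = 23.3% rather than 7/34 = 20.6%.

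**Step 3: effect on the decision, with replacement and an all-treated null.** Put p0/(1 − d) into the formula of step 1:

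| d | A: null rate among evaluable | A: type I error | B: null rate among evaluable | B: type I error |
|---|---|---|---|---|
| 0 | 5.00% | 5.8% | 13.30% | 9.2% |
| 5% | 5.26% | 6.8% | 14.00% | 11.3% |
| 10% | 5.56% | 7.9% | 14.78% | 14.0% |
| 15% | 5.88% | 9.3% | 15.65% | 17.4% |
| 20% | 6.25% | 11.0% | 16.63% | 21.6% |

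The 10% target is passed at d of about 17% in Cohort A and about 2% in Cohort B.

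**Step 4: effect on the decision, without replacement.** Under Protocol 8.2, 30 treated patients yield responses at the all-treated rate, and excluded patients add none. The count rules applied to those 30 keep 5.8% and 9.2%. Only the estimate moves: at d = 10%, three of 30 are excluded and four responses read as 4/27 = 14.8% instead of 4/30 = 13.3%.

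**The case against.** The strongest defence is that an evaluable-set primary is a prespecified and common choice for an open-label go/no-go design. Protocol 5.2 defines the Simon stages on evaluable patients, so the stated error rates are right for the population named. SAP 5 also tabulates removals from each set, so exclusions will be visible. This stands, and it is why the evaluable-set ORR need not be discarded. It does not supply an ORR rule for lost patients or an estimate for all treated patients.

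Four stronger readings are tempting, and the documents do not support them.

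- A reader might infer that everyone who stops for toxicity drops out of the ORR. Protocol 9.1.1 keeps such patients on scheduled scans until progression, new therapy, withdrawal or death. They are excluded only if the Week 12 scan is missing.
- A reader might infer that the stated type I errors are wrong. They reproduce. They fail only if excluded patients are replaced and the null is an all-treated rate. The Cohort B null equals the 13.3% nivolumab ORR quoted in Protocol 3.2.1.1, but nothing says it was taken from there or on what denominator.
- A reader might infer that replacement is settled. Protocol 8.2 contradicts it.
- A reader might infer that SAP 9.1 flatly contradicts SAP 4. Its line on lost patients is general and can be read as covering safety analyses and listings. The fair criticism is that the promised ORR rule is absent.

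The sentence quoted from Protocol 10.3 also covers, taken alone, only patients with no post-baseline assessment at all. Someone with a Week 6 scan only is excluded by the Week 12 requirement, not by that sentence, so the wording is ambiguous there too. The DCR rule is an imperfect precedent, because SAP 7.1 places DCR on the same evaluable set.

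**Conclusion.** The point holds for the estimate: relative to all treated patients the primary ORR is inflated by 1/(1 − d), with or without replacement, provided the excluded patients are non-responders. The effect on the decision is conditional. With replacement and an all-treated null, assumed d of 5%, 10% and 20% gives 6.8%, 7.9% and 11.0% in Cohort A, and 11.3%, 14.0% and 21.6% in Cohort B. Cohort B has almost no margin; Cohort A has a good deal. If Protocol 8.2 governs and the counts are taken on 30 treated patients, the error rates stand. The documents give neither d nor the basis of the null rates, so the size cannot be narrowed further. This should be corrected, but it does not invalidate the design.

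**What to change.** 1. In SAP 7.1, prespecify an all-treated ORR beside the evaluable-set ORR: Safety Analysis Set by cohort, no Week 12 assessment counted as non-response, exact 90% CI as already planned. A patient who stops for toxicity but has a Week 12 scan is scored on that scan.
2. Report the Simon decision on both bases, the all-treated one using the first 15 and first 30 dosed patients per cohort.
3. In SAP 9.1, state how a patient lost before Week 12 enters the ORR, as Protocol 10.4 promised. In Protocol 10.3 and SAP 4, make clear where a patient with only a Week 6 scan belongs.
4. Reconcile Protocol 5.2, Protocol 8.2, SAP 2.2 and SAP 9.1 on replacement, dealing explicitly with the safety run-in exception.

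Cost: wording changes, one extra table and a slightly lower second ORR. If the 18% and 29% targets were meant for evaluable patients, the all-treated decision has less power. At p1(1 − d) with d = 10%, the rates are 0.18 × 0.9 = 16.2% and 0.29 × 0.9 = 26.1%, with power 72.4% (A) and 69.1% (B); at d = 20%, power is 62.9% and 55.3%. State this beside the result so that a negative all-treated reading is not over-interpreted.
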